
Risks with Hybrid Closed Loop may include:
 
• Hypoglycemia• Severe hypoglycemia• Hyperglycemia• Diabetic ketoacidosis• User Entry Error
◦ Patient administering boluses by entering false carb doses leading to hypoglycemia or hyperglycemia◦ Patient entering false glucose values for any reason leading to hypoglycemia or hyperglycemia◦ Patient entering false BG values for calibration leading to hypoglycemia or hyperglycemia• Sensor failure resulting from patient failure to calibrate leading to hypoglycemia or hyperglycemia• Sensor over-reading resulting in hypoglycemia• Sensor under-reading resulting in hyperglycemia• Sensor missed transmission, or any other fault resulting in no SG value, leading to hyperglycemia or hypoglycemia• Voluntary insulin delivery (with the pump or with a syringe) immediately prior to entering Auto Mode may result in severe hypoglycemia despite shutting down insulin delivery by the algorithm• Patient takes insulin via injection while in Hybrid Closed Loop (Auto Mode)• Hypoglycemia or hyperglycemia related to entering or exiting Hybrid Closed Loop (Auto Mode)• Insulin over-delivery due to potential interference from acetaminophen	
Prevention and mitigation include:
 
• Follow the provided user guides for insulin pump management.• Training prior to study on device use and diabetes management principles and instructed to call with problems.• Subjects are instructed to check their meter glucose if their high or low symptoms do not match their sensor alerts or sensor glucose readings in order to make diabetes treatment decisions.• Subjects are instructed to check their meter glucose if there are any concerns that the sensor glucose value is not accurate.• Subjects are instructed if there are no sensor values, no treatments decision should be made until a BG is confirmed.• Subjects are instructed to have glucose on hand for hypoglycemia• Subjects will be instructed to consider avoiding the use of products containing acetaminophen.• If acetaminophen is taken, subjects will be instructed to use additional BG meter readings (they are not to calibrate with those readings) to verify their glucose levels.• If acetaminophen is taken, subjects should turn off Auto Correction and consider exiting Auto Mode.

The following risks that apply to the AHCL system are the same as for other commercialized insulin pump models.

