² If an investigational device gives an incorrect diagnosis, the patient might, for example, receive an unnecessary treatment and incur all the risks that accompany that treatment, or might be incorrectly diagnosed with a serious disease. In other cases, the patient might not receive an effective treatment (thereby missing out on the benefits that treatment would confer) or might not be diagnosed with the correct disease or condition.

2) Unlikely: the relationship with the use of the device seems not relevant and/or the event can be reasonably explained by another cause, but additional information may be obtained.

3) Possible: the relationship with the use of the investigational device is weak but cannot be ruled out completely. Alternative causes are also possible (e.g. an underlying or concurrent illness/ clinical condition or/and an effect of another device, drug or treatment). Cases where relatedness cannot be assessed or no information has been obtained should also be classified as possible.

4) Probable: the relationship with the use of the investigational device seems relevant and/or the event cannot reasonably be explained by another cause, but additional information may be obtained.

5) Causal relationship: the event is associated with the investigational device or with procedures beyond reasonable doubt when:

- The event is a known side effect of the product category the device belongs to or of similar devices and procedures;
- The event has a temporal relationship with investigational device use/application or procedures;
- The event involves a body-site or organ that:
 - o The investigational device or procedures are applied to;
 - o The investigational device or procedures have an effect on;
- The event follows a known response pattern to the medical device (if the response pattern is previously known);
- The discontinuation of medical device application (or reduction of the level of activation/exposure) and reintroduction of its use (or increase of the level of activation/exposure), impact on the event (when clinically feasible);
- other possible causes (e.g. an underlying or concurrent illness/ clinical condition or/and an effect of another device, drug or treatment) have been adequately ruled out;
- Harm to the subject is due to error in use;
- The event depends on a false result given by the investigational device used for diagnosis, when applicable;

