- In order to establish the relatedness, not all the criteria listed above might be met at the same time, depending on the type of device/procedures and the event.

Example: A severe hyperglycemia AE with the following event description would have the following causality assessment for device relatedness:

Improved glucose without an infusion set/site change	Not related
Changed infusion set with glucose improvement	Possible
Infusion set fell out, bent cannula, occlusion alarm	Causal relationship

12. Data Review Committees

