12.1. Clinical events Committee

A Clinical Event Committee (CEC) consisting of external physicians with an expertise in endocrinology and the management of diabetes, including insulin pumps and CGM will be convened. The CEC will review on periodic basis AEs as required per protocol, and may include reports of:

- Serious Adverse Event (SAE)
- Serious Adverse Device Effect (SADE)
- Unanticipated Serious Adverse Device Effect (USADE)
- Severe Hypoglycemia
- Diabetic Ketoacidosis (DKA)
- Deaths

The CEC will assess events to determine agreement or disagreement with the investigator classification of an event (e.g. seriousness, relatedness to device and procedure, unanticipated/anticipated). The CEC will only provide three causality assessments for device and procedure relatedness: Not Related, Possible, and Causal relationship.

Causality Categories for Investigational Center		Causality Categories for CEC:

• Not Related• Unlikely• Possible• Probable• Causal relationship		
• Not Related• Possible• Causal relationship

The sponsor will notify the investigator of any disagreement in assessment of an event by the CEC. All other events will be reviewed and classified by the Sponsor's qualified internal safety individual(s) to ensure they should not be adjudicated by the CEC and that the events are appropriately classified by the investigator.

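### The worked causality example in Protocol 11.5 rates severe hyperglycemia that improves without an infusion-set change as Not related, which conflicts with the protocol's own list of sensor, calibration, transmission and Auto Mode causes.

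*Protocol*

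**What the plan says.** The general rules in Protocol 11.5 come first. The site is to consider every element of the event. The rating has five levels, from Not related to Causal relationship. A weak link that cannot be fully excluded is Possible, and "Cases where relatedness cannot be assessed or no information has been obtained should also be classified as possible".

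The section then gives its only worked illustration: "Example: A severe hyperglycemia AE with the following event description would have the following causality assessment for device relatedness". It has three rows:

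- "Improved glucose without an infusion set/site change": Not related.
- Infusion set changed, and glucose improved: Possible.
- "Infusion set fell out, bent cannula, occlusion alarm": Causal relationship.

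The hybrid closed loop risk table in 10.1.1 lists, among other routes to hyperglycemia:

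- "Sensor under-reading resulting in hyperglycemia"
- "Sensor failure resulting from patient failure to calibrate leading to hypoglycemia or hyperglycemia"
- missed sensor transmission, or another fault that leaves no sensor value
- "Hypoglycemia or hyperglycemia related to entering or exiting Hybrid Closed Loop (Auto Mode"

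Section 10.3 adds that the algorithm's automated reduction of insulin delivery may make hyperglycemia more likely.

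**The concern.** The product under test is a closed-loop system: a pump, its algorithm, and the sensor signal that drives it. The example tests for one failure only, that of the infusion set. When that failure is absent, it clears the whole system. A site that reads the table as a lookup would rate as unrelated an event caused by a sensor reading low, or by an Auto Mode exit, provided that glucose came down with the set left in place.

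Two things are at stake. The first is the classification of adverse device effects (ADEs) in a premarket device study. The second is reporting speed. Table 7 in 11.3 gives ADEs a limit of 72 hours. An adverse event that is neither device-related nor serious need only be reported in a timely manner.

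**Working it through.** The plan states no figure on this point, so there is none to reproduce. The check sets the first row of the example beside the other passages that govern the same rating.

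1. **Scope of device.** Section 11.2 applies the word to any device used in the study, including marketed components. Sensor and transmitter faults therefore count as device causes, although both are CE-marked. The row examines the infusion set alone.

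2. **Named risks.** Section 10.1.1 gives four routes to hyperglycemia that do not lie in the set (under-reading, calibration failure, lost transmission, Auto Mode entry or exit), and 10.3 gives a fifth (automated attenuation). The documents do not say how each resolves. Nothing in them suggests that any would need a set change, so improvement without one cannot exclude them.

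3. **Infusion causes.** The infusion risk table in 10.1.1 mentions insulin by pen or syringe for persistent hyperglycemia as an alternative to changing the set. Even an infusion-related event could therefore improve with the set in place and fall into the first row. The row does not reliably exclude the one cause it tests.

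4. **Criteria for Not related.** One criterion in 11.5 is that the event is not a known side effect of the product category. Section 10.1.1 lists hyperglycemia as a risk of hybrid closed loop, so that criterion does not support the row.

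5. **Use error.** Section 11.5 counts harm from error in use towards a causal relationship, and the ADE definition in 11.2 includes use error. A missed calibration that leads to hyperglycemia is such a case, yet the first row can send it to Not related.

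6. **Default for uncertainty.** Under "Cases where relatedness cannot be assessed or no information has been obtained should also be classified as possible", an event with no sensor or Auto Mode information belongs in Possible. The first row rates it Not related.

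7. **Which events are exposed.** Section 11.3.1 requires every severe hyperglycemia event to be recorded as an AE whatever its rating, so total AE counts do not change. Section 12.1 puts SAEs, SADEs and DKA on the Clinical Events Committee's list, where relatedness is assessed again. What remains is severe hyperglycemia that is neither serious nor DKA. It meets the 11.2 definition (glucose above 300 mg/dL with ketones above 0.6 mmol/L or symptoms) and receives the sponsor's internal safety review.

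8. **Size.** The shortfall in ADEs would be N × a × b. N is the number of exposed events with a device cause, a is the share that improve without a set change, and b is the share of those rated by the row instead of by the definitions. The documents give none of the three. The result runs from 0 (b = 0) to N (a = b = 1). Only the direction is determined: any error lowers the ADE count.

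**The case against.** The strongest reply is that the table is labelled an example and follows the operative definitions. Its rows are short descriptions. An event report that records a sensor under-reading or an Auto Mode exit matches none of them, so the general rules would apply. Section 11.3.1 also requires sites to obtain source documents, including device uploads, to support the event. This stands as far as it goes: misclassification depends on sites following the row instead of the definitions. It does not remove the contradiction. This is the only worked causality example in 11.5, it concerns an event that must be reported, and it attaches one fixed rating to each description.

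A reader might infer that SADE or USADE counts are biased. The documents do not support that. ADE is not among the safety endpoints in Protocol 5.3.2.1 or in SAP 7.10.3. SADE and USADE can change only through serious events, and those are on the Clinical Events Committee's list whatever the site's rating.

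A reader might also infer that only sponsor staff oversee these events, because 12.1 says "All other events will be reviewed and classified by the Sponsor's qualified internal safety individual(s". That goes too far. The committee's list is introduced in non-exhaustive terms, the Data Monitoring Committee in 12.2 monitors adverse events, and AEs go to authorities and ethics committees under local rules.

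Finally, faults may reach the sponsor through device deficiency reporting (11.3.2), with immediate reporting where there was SADE potential. This helps only when the site recognises the fault, which the first row does not prompt it to look for.

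**Conclusion.** The internal contradiction is real. The first row of the example in 11.5 cannot be reconciled with 10.1.1, 10.3, the scope of device in 11.2, or the review and Possible rules in 11.5. Applied literally, it may under-classify device-related severe hyperglycemia, mainly non-serious ADEs that are not DKA, and move them from the 72-hour row of Table 7 to the timely-manner row.

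A reader might go further and conclude that device effects in the AHCL arm are in fact under-counted. The documents show only a risk in that direction. Its size depends on event numbers, on how the events resolve, and on site behaviour, none of which the documents give. The primary and secondary efficacy results, total AE counts and the listed SADE and USADE endpoints are not called into question. The conclusion assumes that at least some sites would rate by the example when the event description is brief.

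**What to change.** Reconcile the example with 10.1.1 and the general rules of 11.5 by splitting the first row in two:

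- Glucose improved without a set or site change; the available device uploads and source documents were reviewed; and sensor, calibration, transmission and Auto Mode causes were excluded: Not related.
- Glucose improved without a set or site change, and any of these causes is present or cannot be excluded, or the data are unavailable: Possible or higher.

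The second row only restates the existing Possible rule. No new data collection is needed, since 11.3.1 already names device uploads as supporting documents. The edit should not assume that a recent upload always exists: 9.1 expects roughly monthly uploads, with one before each contact, while 9.8.3 trains subjects to upload weekly.

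Adding severe hyperglycemia to the Clinical Events Committee's list is not needed for this correction. It would be a matter of preference and would add workload.

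The cost is one table edit with a short note to sites, then a few more Possible ratings and 72-hour reports. No endpoint, sample size or treatment rule changes.

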12.1. Clinical events Committee

A Clinical Event Committee (CEC) consisting of external physicians with an expertise in endocrinology and the management of diabetes, including insulin pumps and CGM will be convened. The CEC will review on periodic basis AEs as required per protocol, and may include reports of:

- Serious Adverse Event (SAE)
- Serious Adverse Device Effect (SADE)
- Unanticipated Serious Adverse Device Effect (USADE)
- Severe Hypoglycemia
- Diabetic Ketoacidosis (DKA)
- Deaths

The CEC will assess events to determine agreement or disagreement with the investigator classification of an event (e.g. seriousness, relatedness to device and procedure, unanticipated/anticipated). The CEC will only provide three causality assessments for device and procedure relatedness: Not Related, Possible, and Causal relationship.

Causality Categories for Investigational Center		Causality Categories for CEC:

• Not Related• Unlikely• Possible• Probable• Causal relationship		
• Not Related• Possible• Causal relationship

The sponsor will notify the investigator of any disagreement in assessment of an event by the CEC. All other events will be reviewed and classified by the Sponsor's qualified internal safety individual(s) to ensure they should not be adjudicated by the CEC and that the events are appropriately classified by the investigator.

12.2. Data Monitoring Committee

A Data Monitoring Committee (DMC) consisting of external physicians with an expertise in Endocrinology and the management of insulin-requiring diabetes including pump and CGM therapy, along with an external statistician will be convened to review study progress and safety. Periodic meetings will be scheduled with DMC.

The DMC is established by the sponsor to oversee the following responsibilities:

- Review the interim analysis of effectiveness and safety measures after approximately 32 subjects (16 subjects in the treatment arm and 16 subjects in the control arm) have been randomized and followed up for 6 months.
- Following predefined rules in the DMC charter, implement the assessment of modifications to the trial design. The primary planned modification is a sample size re-estimation.
- Monitor baseline comparability.
- Monitoring adverse events.
- Review aggregate subject data.
- Provide recommendations to continue or terminate the trial depending upon these analyses.

13. Statistical Design and Methods

13.1. Subject Disposition

The number of subjects enrolled, randomized, completed, early terminated the study will be presented. The reasons for discontinuing prior to study completion will be summarized.

13.2. Subject Demographics and Baseline Characteristics

Subject demographics and baseline characteristics will be summarized by descriptive statistics (mean, standard deviation, minimum, median, and maximum) for continuous variables and by counts and percentages for categorical variables.

13.3. Sample Size Considerations

For Cohort A (MDI+FGM), the sample size calculation was performed based on the following assumptions: alpha=0.05, power=80%, 0.7 standard deviation and 0.5 reduction in mean change of HbA1c in the treatment arm, as compared to the control arm, which is the minimum clinically meaning difference. The standard deviation was based on the *Eurythmics study* (Hermanides, 2011) comparing SAP therapy (Treatment arm) vs MDI (control arm) with a pooled standard deviation of 0.83.

Based on these assumptions, the minimum sample size required is 64 subjects (32 in each arm) in Cohort A comparing AHCL with MDI + FGM subjects.

The following drop-out assumptions have been taken into account, based on experience with previous studies: At screening: 10%; After run-in: 5%; During 6-month follow-up: 7.5%.

Incorporating these drop-out rates, a total of 84 subjects need to be screened in Cohort A (AHCL vs MDI+FGM) in order to have 74 subjects starting the run-in phase, 70 subjects randomized to start the treatment phase and 64 subjects to complete the study phase (6 months). To minimize imbalance in the number of subjects across sites, a minimum of 4 and a maximum of 20 subjects of the cohort should be randomized at each site, with the current sample size.

For the exploratory analysis in Cohort B, comparing MDI + CGM versus AHCL, 30 subjects will be required for analysis. Incorporating the expected dropout rates, a total of 40 subjects need to be screened, in order to have 36 subjects starting the run-in phase, 34 subjects randomized to start the treatment phase and 30 subjects to complete the study. Subjects will be randomized in a 1:1 ratio to the 2 arms.

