13.5. Analysis of Primary Endpoint

The primary objective is to compare the mean HbA1c change from baseline to end of study (6 month) between control arm ($\Delta_{\text{HbA1c MDI therapy + FGM}}$) and treatment arm ($\Delta_{\text{HbA1c AHCL}}$). The null hypothesis $H_0: \Delta_{\text{HbA1c MDI therapy + FGM}} = \Delta_{\text{HbA1c AHCL}}$ will be tested against the alternative hypothesis $H_A: \Delta_{\text{HbA1c MDI therapy + FGM}} \neq \Delta_{\text{HbA1c AHCL}}$ using a linear mixed model (random effect model) that uses all available data and account for possible missing at random data. This confirmatory analysis aims at demonstrating the superiority of AHCL and will be performed on the Intent to Treat (ITT) basis. The ITT population will be composed of all randomized subjects irrespective of their compliance to the planned course of treatment or deviations from protocol. Significant between arm difference will be concluded if $P\text{-value} < 0.05$.

Descriptive summary statistics of the primary endpoint will be presented stratified by study phase, treatment arm, investigational (study) site and other variables.

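### Cohort A's 80% power rests on an SD of 0.7, but the trial named as its source has a pooled SD of 0.83, at which 64 completers give about 66%

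*Protocol*

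**What the plan says.** Protocol section 13.3 lists the inputs for Cohort A as "alpha=0.05, power=80%, 0.7 standard deviation and 0.5 reduction in mean change of HbA1c in the treatment arm", relative to control. It calls 0.5 the smallest clinically meaningful difference. The next sentence gives the origin of the SD: "The standard deviation was based on the" cited trial of sensor-augmented pump therapy "vs MDI (control arm) with a pooled standard deviation of 0.83". From these inputs it concludes that "the minimum sample size required is 64 subjects (32 in each arm) in Cohort A". With 7.5% drop-out over six months, this becomes 70 randomised.

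Three other places bear on the point:

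- Section 13.5 states a not-equal alternative, so the test is two-sided. It plans a linear mixed model on the intent-to-treat population and names no baseline covariate.
- Section 13.4 acknowledges uncertainty about the effect and the SD. It plans a conditional-power re-estimation of sample size once at least 32 Cohort A subjects have completed six months.
- SAP section 6.2 repeats the sample size text of 13.3, with both SDs and no explanation.

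**The concern.** Two adjacent sentences give different SDs, and the first is said to come from the second. Nothing in 13.3, 13.4 or SAP 6.2 links them: no rounding rule, correlation, adjustment or second source. The calculation uses the smaller value, which is the favourable one.

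Cohort A is the confirmatory cohort, and HbA1c change is the gatekeeper of the testing sequence in section 13.6. If it is not significant, no secondary hypothesis can be claimed. Ethics committees, the DMC and later readers will take 80% as the chance of detecting the difference that the plan calls the smallest worth detecting. If the SD is the one in the cited trial, the risk of missing that difference is about 34% rather than 20%, and a null result would be given more weight than it deserves.

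**Working it through.** **Inputs** (protocol 13.3 unless noted): difference δ = 0.5; two-sided α = 0.05 (sidedness from 13.5); 1:1 allocation (9.10); n = 32 completers per arm; σ = 0.70 as used, or 0.83 as cited.

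**Method.** Two-sample t-test on HbA1c change. The noncentrality is λ = δ / (σ √(2/n)) on 2n − 2 degrees of freedom. Power is the probability that a noncentral t with this λ exceeds the two-sided critical value.

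**Step 1: reproduce the plan's figure, σ = 0.70.** With n = 32, √(2/32) = 0.25, so λ = 0.5 / (0.70 × 0.25) = 2.857 on 62 df. Power is 80.3%. Solving for 80% gives 31.8, so 32 per arm and 64 in total, as stated. A one-sided test would need only 25 per arm, so the plan's number comes from a two-sided test.

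**Step 2: the cited SD, σ = 0.83.** λ = 0.5 / (0.83 × 0.25) = 2.410 on 62 df. Power is 66.0%. The shortfall against the plan's calculation is 80.3 − 66.0 = 14.3 percentage points.

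**Step 3: variations at σ = 0.83.**

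| Question | Result |
|---|---|
| Power at 32 per arm, t-test | 66.0% |
| Power at 32 per arm, normal approximation | 67.3% |
| Power if all 70 randomised contribute (35 per arm), t-test | 70.0% |
| n per arm for 80% power, t-test | 44.2, so 45 (90 completers) |
| Randomised to obtain 90 completers at 7.5% drop-out | 90 / 0.925 = 97.3, so 98 |

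**Step 4: detectable difference.** At 32 per arm, 80% power needs a standardised difference of 0.7115. At σ = 0.83 that is 0.7115 × 0.83 = 0.59. Read the other way, 32 per arm keeps 80% power for a difference of 0.5 only while σ is at most 0.5 / 0.7115 = 0.703, so the design has almost no margin above 0.70.

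**Step 5: could 0.70 be 0.83 after baseline adjustment?** Suppose 0.83 is the SD of change and HbA1c has equal variance at baseline and six months, with correlation ρ. Adjusting for baseline multiplies the variance of change by (1 + ρ)/2. The ratio needed is (0.70/0.83)² = 0.711, so ρ = 2 × 0.711 − 1 = 0.42. A higher correlation gives a smaller gain: at ρ = 0.6 the adjusted SD is 0.83 × √0.80 = 0.742, and power at 32 per arm is about 75.5%.

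**The case against.** Four points can be made for the plan.

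**The arithmetic is correct for its inputs.** This stands. The sample size follows from 0.70, and both SDs are printed in the open. What is wrong is the attribution of 0.70 to a source reporting 0.83, and the power claim that depends on it.

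**0.83 may not be the comparable quantity.** Section 13.3 does not say whether it is the SD of change, of final HbA1c or of a model residual, and the planned mixed model may be more precise than a t-test on changes. This also stands as a possibility, and a correlation of 0.42 is not implausible. But the plan states no correlation and commits to no baseline adjustment, so the reader cannot get from 0.83 to 0.70. Silence about which SD is meant is a further reason to correct the sentence.

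**66% is the low end.** Partly fair. The intent-to-treat analysis uses all available data, so 66% to 70% is a reasonable range for the fixed design. Its upper end is still 10 points short of the claim.

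**The interim re-estimation covers uncertainty in the SD.** It may raise the sample size, so 66% is the power of a fixed trial with 64 completers, not necessarily of the adaptive one. The rules are in the DMC charter and the protocol gives no target or cap, so the adaptive power cannot be computed from these documents. Simulations at an SD of 0.83 under assumed rules (re-estimation at 16 per arm to 80% conditional power, caps of 48 or 64 per arm, with and without futility stopping) improved on the fixed design but stayed below 80%. The re-estimation softens the consequence. It neither explains 0.70 nor makes 80% the power of 64 completers at 0.83.

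The repeat in the SAP carries less weight. That SAP covers the exploratory continuation phase, and none of its analyses depends on the figure. It matters only because it does not resolve the discrepancy.

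**Conclusion.** The concern holds: section 13.3 is wrong as written. It derives 80% power from an SD of 0.70 and attributes that SD to a trial with a pooled SD of 0.83, without explanation. On the cited SD, 64 completers give 66.0% power for a difference of 0.5 (70.0% with all 70 randomised), and the difference detectable with 80% power is 0.59.

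These figures assume that 0.83 is the SD of HbA1c change, a two-sided 5% t-test with equal arms, and no increase at the interim. Type I error, the treatment estimate and its confidence interval are unaffected. The error lies in the stated power and its justification, not in the sample size arithmetic.

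**What to change.** Correct protocol 13.3 and the matching text in SAP 6.2 in one of two ways.

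1. **State power under both SDs**, for example: *64 completers give 80% power for a difference of 0.5 if the SD of HbA1c change is 0.70, and 66% if it is 0.83 as in the cited trial, where the difference detectable with 80% power is 0.59.*
2. **Justify 0.70.** If it is meant as a residual SD after adjustment for baseline, say so, give the assumed baseline-to-six-month correlation (about 0.42 under equal variances) and name baseline HbA1c as a covariate in section 13.5. If it comes from another source, cite that source.

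In either case, say what kind of SD 0.83 is.

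The cost is a few sentences in each document and, under the first option, a less favourable power figure. The second option may also need a line in the primary model specification. Neither asks for more patients, further procedures or a change to the interim plan.
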